For women of childbearing age with the possibility of pregnancy, a sample of urine will be collected before any study interventions to confirm a non-pregnant state [this is standard for the surgery regardless of study participation]. Study participation will require that women of childbearing age with the possibility of pregnancy use a birth control method, such as abstinence, diaphragm, condom or intrauterine device to prevent pregnancy until lead removal. Anthropomorphic and demographic characteristics as well as baseline end points will be recorded/measured, including a pain score at the surgical site using the Numeric Rating Scale (NRS, 0-10), sensory deficits (measured with von Frey filaments within the cutaneous distribution of the target nerve), and muscle strength (measured with a pressure transducer; **Table 1**).

Table 1. Anatomic locations for electrical leads and peripheral nerve blocks.

Surgical Location	Surgical Procedures	Lead Location	Peripheral Nerve Block Location	Muscle Motion/Strength Tested
Shoulder	• Rotator cuff repair	Brachial plexus roots	Brachial plexus trunks	Shoulder abduction and grip strength
Knee	• Anterior cruciate ligament repair with a patellar autograph	Femoral	Adductor canal	Knee extension
Foot or ankle	• Hallux valgus correction • Ankle arthrodesis/arthroplasty	Subgluteal sciatic	Popliteal sciatic	Plantar flexion

Figure 8. Study protocol

Lead insertion. Insulated leads will be inserted prior to peripheral nerve block administration. The lead insertion sites will be cleansed with chlorhexidine gluconate and isopropyl alcohol, and a sterile, fenestrated drape applied. A portable ultrasound paired with either a linear or curved array transducer within a sterile sleeve will be used for lead insertion (Figure 9). The target nerve will be imaged in a transverse cross-sectional (short axis) view and a local anesthetic skin wheal raised lateral to the ultrasound transducer.

A needle and a pre-loaded, monopolar, helically-coiled, insulated lead (SPR Therapeutics, Cleveland, OH) will be inserted. Using an in-plane ultrasound approach, the needle tip will be advanced to approximately 1-2 cm from the target nerve. The lead will be subsequently attached to an external stimulator (SPR Therapeutics), and a surface return electrode applied. Accurate lead placement will be confirmed with subject reports of comfortable sensations over the surgical site without eliciting muscle contractions.

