Postoperative course. Within the recovery room following surgery, the stimulators will be attached to the leads and activated, followed by end point assessment. Subjects who had a spinal anesthetic will have end points recorded following spinal resolution. Operating and recovery room pharmacologic analgesic requirements will be recorded.

Post-hospital course. Prior to discharge, subjects and their caretakers will be provided with verbal and written stimulator/lead instructions and the telephone and pager numbers of a local investigator available at all times. Subjects will be discharged home with their leads *in situ*, and contacted every-other day by a healthcare provider until lead removal. Subjects will be also be discharged with a prescription for immediate-release oral oxycodone (5 mg tablets taken for breakthrough pain).

Therefore, *all* patients of this study—regardless of the treatment arm they are randomized to—will continue to receive current usual and customary analgesia. Subjects will be contacted by telephone for end point collection. Lead removal will occur on postoperative day 14 (+/- 2 days) by healthcare providers. If the lead is removed following Day 14, the stimulator will be turned off on Day 14 and removed subsequently. Similar to perineural catheters,¹³⁵ this procedure encompasses simply removing the occlusive dressing and gently pulling on the lead. Following study completion, the results will be mailed electronically or by the United States Postal Service to all enrolled subjects in written form using non-technical language.

Outcome measurements (end points). We have selected outcome measures that have established reliability and validity, with minimal inter-rater discordance, and are recommended for pain-related clinical trials by the World Health Organization and the Initiative on Methods, Measurement, and Pain Assessment in Clinical Trials (IMMPACT) consensus statement.¹³⁶ Importantly, nearly all outcome measures are common data elements from the National Institute of Neurological Disorders and Stroke (NINDS).¹³⁷ End points (Table 2) will be evaluated at baseline (prior to surgery on postoperative day 0), during the treatment period (postoperative days 1-14); and the follow-up period (postoperative day 15 and months 1, 4, and 12).

Table 2. Summary of post-enrollment assessments (color added for clarity)

Time Point:	Postoperative Days								Postoperative Months		
	0	1	2	3	4	7	11	15	1	4	12

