Quarterly Total:	0	0	0	0	32	32	0	0	48	48	48	48	48	48	48	48	48	48	48	0	0	0	0	592	
Yearly Total:	0				64				192				192				144				0				

The Study Team (Figure 13). The study team consists of the Principal Investigator, 7 additional members of the Steering Committee, 7 Site Directors, 1 research coordinator for each of the 7 enrolling centers, and 2 Significant Contributors from the company that developed the electrical leads and stimulator.

Statistical Plan and Data Analysis

Randomized groups will be compared for balance on baseline characteristics using descriptive statistics and the standardized difference (i.e., difference in means or proportions divided by pooled standard deviation). Absolute standardized differences larger than 0.10 will be considered imbalanced and the corresponding variables considered for adjustment in all analyses. Primary analyses will be modified intent-to-treat, such that all randomized patients who receive at least some of the study intervention will be included in the analyses. All patients will be analyzed in the group to which they were randomized.

Statistical methods will largely be the same for the Planning Phase and the Implementation Phase. As explained below, one difference is that in the planning phase focus we will be on the estimated confidence interval for the treatment effects and the variability of the outcomes, as these will be used in designing the full trial. Another is that interim analyses and more thorough subgroup analyses will be done in the Implementation Phase. Details are given below.

UG3 Planning Phase. For Specific Aim 2 we will estimate the treatment effect of PNS versus usual and customary care on pain and opioid consumption using a joint hypothesis testing framework. Specifically, we will conclude PNS is superior to usual and customary analgesia, at least one of Hypotheses 1 and 2 must be superior while the other either superior or at least noninferior.

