We will first test for noninferiority of PNS to usual care on each of the two outcomes using 1-tailed noninferiority tests. The noninferiority deltas will be 1 point (worse) in pain score and 20% higher in opioid consumption. Noninferiority will be assessed at the overall 0.05 significance level with no adjustment to the significance criterion for testing two outcomes since noninferiority is required on both outcomes – i.e., an intersection union test. A noninferiority delta of 1 point in pain score is conservative since receiver operating characteristic curve analysis has demonstrated that changes from baseline of at least 1.7 along a 10-point NRS accurately identified patients who rated improvements as “much improved” or more, compared with those who perceived no change or worsening following analgesic interventions.^{153,156,177-179}

We will assess noninferiority on pain score using a one tailed t-test which incorporates the noninferiority delta of 1 point. The estimated treatment effect for pain score will be derived from a linear mixed effects model with the outcome of patient’s “average” pain score for each day, with fixed effects for intervention (PNS vs usual care) and time (days 1 through 7), and assuming an autoregressive correlation structure among and measurements on the same patient overtime. We will then test for noninferiority with a one tailed t-test in which the numerator is the estimated treatment effect from the model minus the noninferiority delta (1), and the denominator is the standard error of the estimated treatment effect. This method will yield results similar to comparing groups on the patient mean of these seven days, but is more flexible since it allows for missing data and also directly accounts for the correlation within patient. The model also allows assessing the treatment by time interaction, but this will most likely not be of interest.^{180,181}

Cumulative opioid consumption is not typically normally distributed, but usually approximates a log-normal distribution. We therefore plan to assess the treatment effect of PNS versus usual care on the log transformed cumulative consumption through POD 7 using a simple linear regression model (equivalent to a t-test). The estimated treatment effect (i.e., difference between groups) will then be used in a noninferiority test with null and alternative hypotheses as: $H_0: \mu_1 - \mu_2 \geq \log(1.2) =$

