Planning Phase sample size considerations. The sample size for the planning phase of 64 patients will be sufficient to estimate the treatment effects of interest with moderate precision, i.e., a confidence interval width of roughly 1.1 standard deviations for each outcome measure. Confidence interval width for a standard deviation estimate will be 0.70 standard deviations. The planning phase will be sufficient to use in estimating the expected treatment effect and standard deviation for each outcome for the larger trial.

UH3 Implementation Phase. Statistical methods for the UH3 Implementation Phase will follow very closely the methods described for the UG3 Planning Phase. The main difference is that UH3 Implementation Phase will have sufficient data to conduct the subgroup analyses and also considerably more power to assess the treatment effects of interest.

Another substantive difference from the planning phase is that in the full trial we will conduct interim analyses at each 25% of the planned enrollment using a group sequential method with gamma spending function and gamma parameter of -4 (quite conservative) for efficacy and 0 (moderately aggressive) for futility (**Figure 14**). The probability of crossing a boundary for either efficacy (mainly) or futility at the first through fourth looks would be 0.10, 0.42, 0.80 and 1.0, respectively, assuming the alternative hypotheses were true.

Figure 14. Stopping boundaries for 1-tailed tests for superiority for either pain score or opioid consumption. Blue region indicates superiority (reduced opioid consumption or pain score) and pink region indicates futility (lack of superiority). Z-statistic represents strength of evidence against the null hypothesis, either ratio of means or difference in means divided by standard error.

Missing outcomes data will be summarized along with the etiology of the absence. | While very little outcomes data is expected to be missing,

analyses will be intention to treat, and imputation of missing data using methods such as multiple imputation and last observation carried forward will therefore be utilized, based on the situation. In a conservative analysis imputation will involve the conservative approach of assigning the worst observed outcome to patients in intervention groups and best observed outcomes to those in control.

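### Neither primary model prespecifies the pre-surgery pain score that the trial already collects; whether it enters depends on chance imbalance and on discretion

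*Combined protocol and SAP*

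**What the plan says.** All references are to section 9 of the combined protocol and SAP.

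- **Pain model** (Statistical Plan and Data Analysis, UG3 Planning Phase): a linear mixed model of each day's average pain score, "with fixed effects for intervention (PNS vs usual care) and time (days 1 through 7", with an autoregressive correlation structure. No baseline term is listed.
- **Opioid model** (same part): log cumulative consumption through day 7 is compared "using a simple linear regression model (equivalent to a t-test". Treatment is the only term.
- **Carried into the main trial** (UH3 Implementation Phase): "Statistical methods for the UH3 Implementation Phase will follow very closely the methods described for the UG3 Planning Phase".
- **What is collected** (Enrollment): "baseline end points will be recorded/measured, including a pain score at the surgical site using the Numeric Rating Scale (NRS, 0-10". Outcome measurements adds that end points "will be evaluated at baseline (prior to surgery on postoperative day 0". Table 2 marks average and worst pain at day 0, and Demographic and medical history lists preoperative least, average, worst and current NRS.
- **The adjustment rule** (opening paragraph of the Statistical Plan): "Absolute standardized differences larger than 0.10 will be considered imbalanced and the corresponding variables considered for adjustment in all analyses".

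**The concern.** The preoperative average NRS is the same item, at the same body site, as the primary pain outcome. It is a reasonable candidate predictor, and section 10 leaves it free to vary, since it excludes long-standing pain only at sites other than the surgical one. If it is prognostic, putting it in the model removes between-patient variation from the treatment estimate at the cost of one degree of freedom.

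The plan instead makes entry depend on observed imbalance. That raises two issues. First, a covariate improves precision because it predicts the outcome, whether or not the arms happen to differ on it; a trigger based on imbalance will usually leave it out of the larger trial. Second, the primary model is not fixed in advance. The rule says only that a flagged variable is considered, and the flag can change as enrolment grows, so successive interim tests might use different models. The pilot could also be adjusted and the main trial not, although pilot estimates are meant to size the main trial.

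**Working it through.** **1. Reproduce the plan's sample size without the covariate.** Inputs from the UH3 sample size text: a coefficient of variation of 75% (the value attached to this calculation), a 20% relative reduction, one-tailed alpha 0.0125 per superiority test, 90% power and 1:1 allocation.

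- Log-scale SD = sqrt(ln(1 + 0.75²)) = 0.668; effect = ln(0.8) = −0.223.
- n per arm = 2 × 0.668² × (2.241 + 1.282)² / 0.223² ≈ 223, so N = 446 by the normal formula and 448 by the noncentral t. The plan states 448.
- Four equally spaced looks with gamma −4 for efficacy and gamma 0 for non-binding futility give an inflation of 1.177, and 448 × 1.177 = 527.1. The plan states 528.
- Pain: SE = 2 × sqrt(2/264) = 0.174. Power for a 1-point effect at one-tailed 0.0125 is about 0.9998.

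The planned figures stand on unadjusted SDs.

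**2. How often would the imbalance rule flag baseline pain?** With n per arm under simple randomization, the standardized difference has standard error of about sqrt(2/n). So P(|d| > 0.10) = 2 × [1 − Φ(0.10 / sqrt(2/n))].

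| Point in the programme | Total N | n per arm | P(flagged) |
|---|---|---|---|
| UG3 pilot | 64 | 32 | 0.69 |
| UH3, 25% look | 132 | 66 | 0.57 |
| UH3, 50% look | 264 | 132 | 0.42 |
| UH3, 75% look | 396 | 198 | 0.32 |
| UH3, final | 528 | 264 | 0.25 |

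Baseline pain would go unflagged in about three final UH3 analyses out of four. Blocked, stratified allocation changes these figures somewhat, so they are approximate.

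**3. What would prespecified adjustment gain for pain?** Let rho be the correlation between baseline pain and a patient's mean score over days 1-7. The plan says its mixed model behaves much like a comparison of patient means, so the adjusted variance is roughly the unadjusted variance times (1 − rho²). The documents give no rho, so the range below is assumed. SE = 0.174 × sqrt(1 − rho²); equivalent unadjusted N = 528 / (1 − rho²).

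| Assumed rho | Variance reduction | SE of pain effect (points) | Equivalent unadjusted N |
|---|---|---|---|
| 0 | 0% | 0.174 | 528 |
| 0.1 | 1% | 0.173 | 533 |
| 0.2 | 4% | 0.171 | 550 |
| 0.3 | 9% | 0.166 | 580 |
| 0.4 | 16% | 0.160 | 629 |
| 0.5 | 25% | 0.151 | 704 |

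**4. Opioid use, conditionally.** If baseline pain had the same correlation with log opioid dose, which is a second assumption, power at 224 per arm in the fixed design (before interim adjustment) would go from 0.902 to 0.905, 0.914, 0.928, 0.947 and 0.967 for rho from 0.1 to 0.5.

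**5. Day 0.** Under Hypothesis 2 the primary pain end point is the mean of average scores over days 0-7, whereas the mixed model uses days 1-7. Outcome measurements places the day-0 assessment before surgery, while the text on postoperative recording also mentions baseline end points. If day 0 is the pre-surgery score, the Hypothesis 2 definition places the proposed covariate inside the outcome.

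**The case against.** The strongest reply is that the plan does provide for baseline adjustment, in all analyses. A reader might infer from the two model descriptions that baseline pain is shut out, or that any chance difference in it passes unchecked into the pain effect. The imbalance rule contradicts both readings. With an outcome SD of 2, a difference just under the threshold shifts the pain effect by at most rho × 0.10 × 2, which is 0.06 points at rho 0.3 and 0.10 at rho 0.5, against a 1-point margin. Larger differences are flagged. This stands. It leaves untouched the discretion in the rule and its reliance on imbalance instead of prognosis. In the pilot, a one-standard-error difference (0.25 SD) at rho 0.4 is worth 0.25 × 0.4 × 2 = 0.2 points, and the plan does not say whether it would be adjusted away.

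A reader might also infer that the trial is biased or underpowered. It is neither: randomization makes the unadjusted comparison unbiased, and the stated N reproduces.

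The size of the gain is assumed, not documented, and at rho of 0.2 or below it is small. Nothing in the documents shows that preoperative pain predicts pain after a new operation with a nerve block. For opioid use the score is not a baseline of the outcome at all. These limits stand.

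Finally, the plan intends to revise the UH3 statistical section after the pilot, which could supply rho. That is a useful opportunity, but the revision is described in terms of treatment effects, group means and sample size parameters, and does not mention covariates.

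**Conclusion.** The point holds as a free precision improvement, not as an error in a stated figure. Neither primary model prespecifies the collected pre-surgery score, and the rule that could bring it in is discretionary and driven by chance: flagged about 25% of the time at N=528 and about 69% at N=64, under simple randomization. The benefit for pain ranges from nothing to a 25% variance reduction over an assumed rho of 0 to 0.5, and is material only from about 0.3. Pain superiority power is already about 0.9998 under the plan's assumptions, so the practical value lies in tighter intervals, more informative pilot estimates, a model fixed before the data are seen, and possibly opioid power.

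**What to change.** Add to the statistical section:

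- The pre-surgery, pre-block average NRS at the surgical site is a fixed covariate in the primary pain mixed model (outcome days 1-7) and in the log-opioid regression, in UG3 and UH3 and at every interim look, whatever the observed imbalance. For this variable it replaces the 0.10 trigger.
- The unadjusted models are kept as sensitivity analyses.
- The Hypothesis 2 definition (days 0-7) and the model (days 1-7) are reconciled, with a statement of which day-0 score is the baseline, so that the same score is not both covariate and outcome.
- The pilot reports the correlation of baseline pain with each primary outcome, so that the UH3 revision can rest on an estimate.

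The cost is a few sentences and one degree of freedom per model. No new data, visits or subjects are needed, and the planned sample size can stay as it is.

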Current/present, worst, least, and average pain at the surgical site will be assessed using a Numeric Rating Scale (NRS) as part of the Brief Pain Inventory (short form). The Brief Pain Inventory is an approved NINDS common data elements Scale. The use of single items (e.g., average pain) in addition to the composite score is supported by the IMMPACT recommendations for assessing pain in clinical trials. The NRS will be recorded at all time points (**Table 2**), ***with the primary end point being the mean value of the “average” pain scores for postoperative days 0-7*** (see statistical section for further details). The NRS is a highly-sensitive measure of pain intensity with numbers

ranging from 0 to 10, zero equivalent to no pain and 10 equivalent to the worst imaginable pain. The NRS has been demonstrated to be a valid and reliable measure following analgesic interventions. In addition, NRS scores correlate well with other measures of pain intensity, and demonstrate high test-retest reliability. These NRS characteristics led to recent IMMPACT consensus recommendations for use of the 10-point NRS of pain intensity for pain trials.

An additional instrument, the Defense and Veterans Pain Rating Scale (DVPRS), will be utilized at various time points following surgery. The DVPRS was developed specifically for—and subsequently validated in—active duty military and Veteran patient populations. Unfortunately, this new instrument has not been validated for repeated measures, and therefore will not be used as a primary end point for the current investigation. However, future pain-related investigations involving military personnel and Veterans will undoubtedly use the DVPRS, and we want the results of the current study to be comparable. Therefore, we will use the DVPRS as a secondary end point at various time points (not all to lessen the questionnaire burden on subjects).

Primary end point: *In order to claim that percutaneous PNS is superior to usual and customary analgesia, at least one of Hypotheses 1 and 2 above must be superior while the other either superior or at least noninferior.*

Hypothesis 3 (UH3): Physical and emotional **functioning** will be significantly improved in the 12 months following ambulatory surgery with percutaneous PNS as compared with usual and customary analgesia (measured with the Brief Pain Inventory).

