Throughout, the significance level will be 0.05 for each hypothesis. SAS statistical software (Cary, NC) will be used for all analyses, and East 6.0 (Cytel, Inc. Cambridge, MA) for interim monitoring and sample size calculations.

UH3 Implementation Phase sample size considerations. Sample size parameters for the implementation phase will be derived from estimates in the planning phase. The sample size calculations below are conservative in that we observed a coefficient of variation for opioid consumption observed in our preliminary data of 0.48, substantially better than the assumed 0.65. It is thus quite possible that the actual sample size for the implementation phase will be smaller.

Sample size for the full trial will be chosen to allow an overall 90% power at the 0.025 significance level (since 1-tailed tests) to claim the intervention more effective than the control on postoperative opioid requirements and pain as measured by NRS pain score. In our joint hypothesis testing on these two outcomes, we power the study to have overall 90% power to detect superiority on either

outcome and at least noninferiority on both. We assume a coefficient of variation of 1.0 for opioid consumption and a standard deviation of 2 for pain score.

Power for the joint hypothesis testing will be driven by superiority tests since superiority is needed for at least 1 of the 2 outcomes. For cumulative opioid consumption through POD 3 our previous data had a coefficient of variation (CV) of 46% (mean (SD) of 28 (13) mg). Conservatively assuming a coefficient of variation of 75% through 7 days,¹⁸³ with a total N=528 we would have 90% power to detect a relative reduction of 20% in mean opioid consumption at the overall 0.025 significance level (0.0125 for each of the two 1-tailed tests for superiority), adjusting for interim analyses (N=448 before adjustment for interim analyses).

This sample size will yield high power (>0.95%) to detect superiority based on the intervention group having 1 point or more better than the control group on NRS pain score within the first 7 days, assuming a standard deviation of 2 points for mean of the “average” pain score for each patient.

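### If the autoregressive term is the only within-patient correlation in the primary pain model and patients differ persistently, the standard error is too small; the visit weighting and endpoint window also need stating

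*Combined protocol and SAP*

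**What the plan says.** Three parts of section 9 bear on this.

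- **Endpoint (Hypothesis 2).** The primary pain endpoint is the "mean value of the “average” pain scores for postoperative days 0-7".
- **Model (Statistical Plan, UG3 Planning Phase).** The daily average score is modelled "with fixed effects for intervention (PNS vs usual care) and time (days 1 through 7" as the levels of time. For dependence within a patient, the plan offers one phrase: "assuming an autoregressive correlation structure among and measurements on the same patient overtime". The plan adds: "This method will yield results similar to comparing groups on the patient mean of these seven days". On day-specific effects it says: "The model also allows assessing the treatment by time interaction, but this will most likely not be of interest". The order of the autoregression, its time scale, any random effect and the type of standard error are not stated. The UH3 methods are said to follow the UG3 methods very closely.
- **Schedule (Table 2).** The column header reads "0 1 2 3 4 7 11 15 1 4 12", the last three being months. Within days 1-7, pain is therefore collected on days 1, 2, 3, 4 and 7 only.

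Pain noninferiority is tested one-tailed at 0.05 with a margin of 1 point. Superiority uses "0.0125 for each of the two 1-tailed tests for superiority".

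**The concern.** A purely autoregressive structure makes correlation die away with lag. Postoperative pain usually also has a lasting patient component. Here the trial pools shoulder, knee and foot/ankle surgery across seven centers. Randomization is stratified by center and lead location, but the pain model contains neither factor, so those differences stay in the residual and do not decay. A model that cannot represent them treats five scores from one patient as more informative than they are.

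The pain tests feed the joint primary claim (noninferiority on both outcomes, superiority on at least one), and the same standard error would enter the interim Z-statistics. A larger sample does not help, because the shortfall is a large-sample limit.

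The second issue is the target. One common coefficient under an autoregressive structure is a weighted average of the daily differences, and the correlation sets the weights. Nothing ties those weights to the defined endpoint.

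**Working it through.** **The plan's own figures.** With 264 per arm, a difference of 1, SD 2 and one-sided 0.0125, the noncentrality is 1/(2 × √(2/264)) = 5.74 and power is 0.9998. This agrees with the plan's figure, printed as >0.95% and evidently meaning 0.95. The opioid sample size (20% reduction, CV 0.75, 90% power, one-sided 0.0125) comes out at 446 against the stated 448 before interim adjustment.

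**Weights.** For AR(1) by visit order over five visits with correlation ρ, days 1, 2, 3, 4 and 7 are weighted 1 : 1−ρ : 1−ρ : 1−ρ : 1. Days 1 and 7 each get 1/(5 − 3ρ), and days 2-4 each get (1−ρ)/(5 − 3ρ). At ρ = 0.5 this is 28.6% and 14.3%; at ρ = 0.7 it is 34.5% and 10.3%. Equal weighting would be 20% each.

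**Standard error under constant correlation c (assumed).** The best-fitting visit-order AR(1) has ρ = c. Per unit variance:

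- model variance = (1+ρ)/(5 − 3ρ)
- true variance = c + (1−c) × Σw²
- actual one-sided error = P(Z > z × SE ratio), with z = 2.241 for 0.0125 and 1.645 for 0.05

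| c | Model variance | Σw² | True variance | SE ratio | 0.0125 becomes | 0.05 becomes |
|---|---|---|---|---|---|---|
| 0.4 | 1.4/3.8 = 0.368 | 0.213 | 0.528 | 0.835 | 3.1% | 8.5% |
| 0.5 | 1.5/3.5 = 0.429 | 0.224 | 0.612 | 0.837 | 3.0% | 8.4% |
| 0.6 | 1.6/3.2 = 0.500 | 0.242 | 0.697 | 0.847 | 2.9% | 8.2% |

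Simulated REML fits at N = 528 and c = 0.5 (20,000 trials) gave an SE ratio of 0.84 and rejection rates of 3.0% and 8.3%. These rates are for a single look and do not include the interim spending.

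**Other assumed truths, same visit-order AR(1) model.**

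- Random intercept (share 0.3-0.5) plus calendar-day decay (0.5-0.7): SE ratio 0.92-0.97; 0.0125 becomes 1.5-1.9% and 0.05 becomes 5.5-6.4%. Simulation at share 0.5 and decay 0.5 gave 2.0% and 6.4%.
- Pure calendar-day decay (0.5-0.9): SE ratio 1.00-1.01; 0.0125 becomes 1.21-1.23%. The error is nominal.

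**Other fitted models.**

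- Calendar-day AR without an intercept, truth constant 0.5: SE ratio 0.80; 0.0125 becomes about 3.7%. Correcting the spacing alone does not help.
- Random intercept plus calendar-day AR: SE ratio 0.96-1.01 across the simulated truths; 0.0125 gives 0.8-1.9%. With 1,500 trials each, the simulation error is about √(0.0125 × 0.9875/1500) = 0.3 percentage points, so this is near nominal.

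**Target (assumed effect patterns).**

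| Effect on days 1, 2, 3, 4, 7 | Mean of collected scores | Model, ρ = 0.5 | Model, ρ = 0.7 |
|---|---|---|---|
| Constant −1 | −1.00 | −1.00 | −1.00 |
| Linear fade from −1.5 to −0.3 | −1.02 | −0.99 | −0.96 |
| 0, −1.2, −1.5, −1.5, −0.3 | −0.90 | −0.69 | −0.54 |

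If day 1 shows no effect and the other days show 1 point, the mean is 0.80 and the model at ρ = 0.5 gives 1 − 0.286 = 0.71.

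**The case against.** The strongest reply is that the plan calls this a linear mixed effects model and says that it accounts directly for within-patient correlation. A random patient intercept with autoregressive residuals fits those words, and the error would then be near nominal. This stands: the documents show under-specification, not a proven error. But the type I error of a primary test depends on the choice, so it should not be left open.

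A reader might infer that the uneven visits cause the small standard error. They do not. Under pure calendar-day decay the visit-order model is nominal, and fixing the spacing alone slightly worsens the ratio under constant correlation (0.80 against 0.84). Spacing affects the weights only.

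A reader might also infer that the plan equates its estimate with the patient mean. It claims only similarity, and the two agree when the effect is constant. With no effect on any day, the weights create no bias; in the patterns above they shrink the apparent benefit.

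Nor are equal weights on five visits the documents' own standard. If days 5 and 6 were filled in linearly, a seven-day mean would give day 7 a weight of 2/7 = 28.6%, the same as the model at ρ = 0.5. The heavy weight on day 1 remains (28.6% against 1/7 = 14.3%). A weak day-1 effect while the nerve block lasts is plausible but assumed, because no block duration is given.

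**Conclusion.** The point holds conditionally. If the autoregressive term is the sole correlation term and patients differ persistently, the pain tests are anti-conservative. One-sided 0.0125 becomes about 1.5-3.1% and one-sided 0.05 about 5.5-8.5%, the upper ends requiring constant correlation with no decay. Among the truths examined, the error was nominal or inflated and never materially conservative. The documents do not support saying that the error rate is definitely inflated, because they give no within-patient correlation and do not rule out a random intercept.

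The departure from the mean of the collected scores is a separate and milder matter that arises only when the effect changes over days. Power for the 1-point difference is not at risk: allowing for the model's weights (SD 2.03 instead of 2), it stays above 0.999. The mismatch between days 0-7, days 1-7 and the five collected days is in the documents whatever the correlation.

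**What to change.** In the Statistical Plan, for the pain model:

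1. Specify an unstructured covariance over the collected visits, with day and treatment-by-day terms. A random intercept plus calendar-time autoregression with robust standard errors is an acceptable alternative.
2. Define the tested effect as a pre-stated average of the daily treatment differences, with the weights written down, and use it for noninferiority, superiority and the interim Z-statistics.
3. Adjust for the baseline pain score, which is already collected.
4. Reconcile the window across Hypothesis 2 (days 0-7), the model (days 1-7) and Table 2 (days 1, 2, 3, 4 and 7), so that the average tested is the defined endpoint. State the role of day 0: section 9 places the baseline assessment there, before surgery, and the same score should not be both covariate and outcome.

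The cost is small. Unstructured covariance needs 5 × 6/2 = 15 parameters against 2 for AR(1), which 528 patients support easily, plus slightly more analysis work. No new data and no change in sample size are needed.
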